2.4 Randomization and Blinding

This is an open-label study.

2.5 Protocol Versions

Study enrollment started on protocol version v3.0 04NOV2015. The current protocol version is version 6.0 dated 30 Jul 2018.

2.6 Protocol Amendments

There are 7 versions of the protocol:

Protocol Version	Version Date
Version 1 – Original protocol	25SEP2015
Version 2	05OCT2015
Version 3	13OCT2015
Version 3.1	04APR2016
Version 4	20APR2016
Version 4.1 – French Protocol Amendment	12MAY2017
Version 5	06APR2018
Version 6	30JUL2018
Version 7	19MAR2019

2.7 Schedule of Assessments

Table 1 Schedule of Assessments – Part B (24-weeks Treatment/ 4-weeks Follow Up)

	Screen	Day 1, Week 1 Pre-dose	Day 1 Week 1 Post-dose ^a	Day 2, Week 1 ^g	Day 15, Week 3 +/- 3 days	Day 29, Week 5 +/- 3 days	Day 57, Week 9 +/- 7 days	Day 85, Week 13 +/- 7 days	Day 113, Week 17 +/- 7 days	Day 141, Week 21 +/- 7 days	Day 169, Week 25 +/- 7 days	Day 197, Week 29 +/- 7 days	Unscheduled Visit
Informed Consent ^k	X												
Inclusion/Exclusion Criteria	X	X											
Height	X												
Weight	X	X			X	X	X	X	X	X	X	X	X
Physical exam/med. History PDAI/ABSIS	X												
Abbreviated physical exam, PDAI, ABSIS		X			X	X	X	X	X	X	X	X	X
ECG (12-lead)	X												(X) ^b
Vital Signs ^j	X	X		X	X	X	X	X	X	X	X	X	X
Urinalysis	X												
Hep B & C, HIV, T- spot TB Test, QuantiFERON®-TB Gold, QuantiFERON®-TB Gold Plus (QFT Plus)	X												
Pregnancy test ^c	X	X				X	X	X	X	X	X	X	
Skin biopsy ^d	X												
Hem, Coag, Chem	X ^e	X			X	X	X	X	X	X	X	X	X
FSH ^f	X												
BTK occupancy sample		X ^g	X ^h	X	X	X	X	X	X	X	X		(X) ^b
PK sample		X	X ^h	X ^a	X	X	X	X	X	X	X		(X) ^b
Anti-DSG antibodies		X				X	X	X	X	X	X	X	

	Screen	Day 1, Week 1 Pre-dose	Day 1 Week 1 Post-dose ^a	Day 2, Week 1 ^b	Day 15, Week 3 +/- 3 days	Day 29, Week 5 +/- 3 days	Day 57, Week 9 +/- 7 days	Day 85, Week 13 +/- 7 days	Day 113, Week 17 +/- 7 days	Day 141, Week 21 +/- 7 days	Day 169, Week 25 +/- 7 days	Day 197, Week 29 +/- 7 days	Unscheduled Visit
Photography (Optional) ⁱ		X			X	X	X	X	X	X	X	X	X
ABQOL & TABQOL		X			X	X	X	X	X	X	X	X	X
SNAQ questionnaire		X				X	X	X	X	X	X	X	X
AEs		X		X	X	X	X	X	X	X	X	X	X
Concomitant Medications	X	X		X	X	X	X	X	X	X	X	X	X
Drug dispensed		X				X	X	X	X	X			
Drug reconciliation					X	X	X	X	X	X	X	X	

- a. Withhold PRN1008 on morning of Day 2 until PK/PD measurement has been taken as close to 12 hours (when *bid* dosing) or 24 hours (when *qd* dosing) after the prior dose as possible. Where follow-up on Day 2 is not possible, PK/PD samples may be taken on another day in the first week of treatment. On all other days, instruct patient to take PRN1008 in the morning as usual prior to clinic and take note of the time taken. Extra PK/PD sample intended for 1 to 5 days after dose adjustment or to replace missing samples—not required for other extra visits.
- b. Only if clinically indicated.
- c. For women of childbearing potential only. Serum pregnancy test done at screening, urine dip test done at other time points.
- d. Performed only if no suitable prior biopsy.
- e. TSH and CPK taken as part of chemistry panel.
- f. To confirm postmenopausal status for women who are not surgically sterile only.
- g. Two-8mL pre-dose blood tubes to be collected at baseline to ensure sufficient samples for later time point assay calculations.
- h. 2 hours post-dose (+/- 15 mins)
- i. Photography is used to document skin disease changes; ideally in most patients. Strict masking of patient identity is required.
- j. Vital sign include blood pressure (BP), pulse rate, body temperature and respiratory rate and are recorded at the time points specified
- k. The Schedule of Assessments has been revised to be consistent with the 24 week treatment duration and 4 week safety follow up assessments described in this protocol Version 5, Part B. Patients enrolled in an earlier protocol version (Part A) who are in the active12-week treatment period are eligible to continue treatment, initially at their current dose, for up to a total of 24 weeks active treatment upon review and signature of the Part B EC approved Patient Informed Consent Form, with procedures and tests per this Schedule. Patients that have completed **Part A** of the trial are also eligible to be screened as a **Part B** patient, upon review and signature of the *Part B* EC-approved Patient Informed Consent Form.

3 ANALYSIS CONSIDERATIONS

3.1 Type of Analyses

The analyses and documentation described in this SAP are for the final analysis of Part B of the study.

3.2 Analysis Populations

3.2.1 Screening Population

All patients who provide informed consent and have screening assessments in Part B evaluated for study participation will be included in the Screening Population.

3.2.2 Safety Population

All patients who received at least one dose of PRN1008 in Part B will be included in the safety population. The Safety population will be used for all safety analyses.

3.2.3 Efficacy Analysis/Intent-to-Treat (ITT) Population

All patients who received at least one dose of PRN1008 in Part B will be included in the Efficacy/ITT analysis population.

3.2.4 Modified Intent-to-Treat (mITT) Population

Patients treated up to Week 5 and had a Week 5 disease assessment will be included in the mITT population.

3.2.5 Completer Population

Patients treated up to Week 25 and had a Week 29 disease assessment will be included in the Completer population.

3.2.6 Per-Protocol (PP) Population

The PP population will include patients who had:

- 1) No major protocol deviations relevant to data integrity per Medical Monitor review
- 2) At least 80% compliance based on drug accountability
- 3) Completed Week 29 visit.

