APPENDIX 1A CORTICOSTEROID RESCUE CRITERIA AND TREATMENT PROTOCOL (PART A)

Systemic corticosteroids will be avoided during PRN1008 monotherapy unless these rescue criteria are triggered, as described below, or if patients enter the study on low doses (≤ 0.5 mg/kg mg per day). In each rescue scenario, the recommended method of corticosteroid taper is shown in [Appendix 7](#).

Rescue Criteria #1: Flare which, in the mind of investigator, is potentially life threatening

- Commence conventional immunosuppressive therapy and discontinue PRN1008

Rescue Criteria #2: Development of severe but not life-threatening PV (defined as PDAI score ≥ 45) at any time during PRN1008 therapy:

- If most recent BTK trough occupancy was 50% or more, commence conventional immunosuppressive therapy and discontinue PRN1008
- If most recent BTK trough occupancy was $< 50\%$ and PRN1008 dose has not been increased since last BTK assay, commence, or increase dose to, full-dose prednis(ol)one (1.0 mg/kg) orally and increase dose of PRN1008 by an amount agreed to with the Sponsor's Medical Monitor. At next review:
 - If not responding, commence conventional immunosuppressive therapy and discontinue PRN1008
 - If responding, maintain or taper corticosteroids as clinically appropriate while maintaining PRN1008 treatment
- If no BTK trough occupancy is available to guide therapy, maintain PRN1008, and commence, or increase to, full-dose prednis(ol)one (1.0 mg/kg) orally. Seek to expedite latest BTK trough occupancy test result or arrange for a new blood draw to measure BTK trough occupancy. At next review:
 - If not responding, commence conventional immunosuppressive therapy and discontinue PRN1008
 - If responding, maintain or taper corticosteroids as clinically appropriate while maintaining PRN1008 treatment (including adjust dose upwards if BTK trough occupancy $< 50\%$ in consultation with the Sponsor Medical Monitor)

Rescue Criteria #3: Patients with non-severe PV but who fail to achieve “Control of Disease Activity (CDA*)” by 4 weeks

- If most recent BTK trough occupancy was 50% or more, commence, or increase dose to, low dose prednis(ol)one (0.5 mg/kg) orally. Review after another ~2 weeks:
 - If not responding, commence conventional immunosuppressive therapy and discontinue PRN1008
 - If responding, maintain or taper corticosteroids as clinically appropriate while maintaining PRN1008 treatment

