4.3.5. Per Protocol (PP) Population

Patients who have

- 1) No major protocol deviations relevant to data integrity per Medical Monitor review
- 2) At least 80% compliance based on drug accountability
- 3) Completed Week 13/Day 85 visit.

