2.3 Expected Sample Size

Sample size for this pilot study was determined pragmatically by the number of subjects required to determine a preliminary safety profile and a point estimate for the primary endpoint of efficacy. If the clinical response rate is 50%, 25 subjects in each Part will result in an 80% CI of $\pm 13\%$. Results from this pilot study will be used to design confirmatory clinical trials.

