5.4.1 Primary Efficacy Endpoint

The primary efficacy endpoint is:

- The proportion of patients who are able to achieve CDA within 4 weeks (on or prior to Week 5 visit) of starting PRN1008 treatment **without** the need for doses of prednis(ol)one > 0.5 mg/kg

The Control of Disease Activity (CDA) responses are assessed at visits specified in the Schedule of assessments (Table 1). Types of CS other than prednis(ol)one are converted to dose-equivalent prednis(ol)one (see Section 5.4.2.3).

This is operationalized as meaning the first CDA is achieved on or before the Week 5 visit but after first dose of PRN1008, and will be summarized, by dose level to the Week 5 visit and overall in a table, using frequencies and percentages. In addition, two-sided 80% and 95% CIs (Confidence Intervals) of the response rate will be provided for each dose level and overall.

Patients who are able to achieve CDA between first dose of study drug and the Week 5 visit without prednis(ol)one >0.5 mg/kg on the date prior to the CDA will be considered as responders, even if the CDA status was not maintained or higher doses of prednis(ol)one were used after the first CDA. Patients who are not able to achieve CDA prior to or at the Week 5 visit or had prednis(ol)one >0.5 mg/kg on the date prior to CDA will be considered as non-responders. Patients whose CDA status is unknown at the Week 5 visit for whatever reason (including early termination before Week 5 visit) will be also considered as non-responders. Only systemic CSs (as defined by medication taken orally or intravenously) are to be used to evaluate the efficacy endpoints, topical CSs (including buccal CS) will not be counted.

The number and percentage of patients who meet the primary efficacy endpoint criteria will be tabulated by dose level and overall (all patients).

A sensitivity analysis using the Completer and PP population will be provided.

Panel plots will be provided for PDAI score over the study period for each patient. Dose level (mg/day) will also be plotted on the same figure. Lines for the steroid equivalent dose in mg/kg will be added to the plots. A total of 9 plots (3 x 3) will be fitted on one page.

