Listing B.16.2.8.6	Serum Chemistry Results – Patients with Abnormal Results (Safety Population)	159
Listing B.16.2.8.7	Urinalysis Results (Safety Population)	159
Listing B.16.2.8.8	Urinalysis Results – Patients with Abnormal Results (Safety Population)	159
Listing B.16.2.8.9	Drug Induced Liver Injury (DILI) Test Results (Safety Population)	159
Listing B.16.2.8.10	Drug Induced Liver Injury (DILI) Test Results – Patients with Abnormal Results (Safety Population)	159
Listing B.16.2.8.11	Anti-DSG Antibodies Results (ITT Population)	160
Listing B.16.2.8.12	PK and BTK Sample Collection (ITT Population).....	161
Listing B.16.2.8.13	Vital Signs and Body Weight (Safety Population)	162
Listing B.16.2.8.14	Vital Signs – Blood Pressure and Pulse – Patient with Abnormal Results (Safety Population).....	163
Listing B.16.2.8.15	12-Lead ECG Results (Safety Population)	164
Listing B.16.2.8.16	12-Lead ECG Results – Patient with Abnormal Results (Safety Population).....	165
Listing B.16.2.8.17	Physical Examination (Safety Population)	166
Listing B.16.2.8.18	Physical Examination – Patients with Abnormal Results (Safety Population)	167
Listing B.16.2.8.19	Pregnancy Test Results (Safety Population)	168
Listing B.16.2.8.20	Food Intake (Safety Population)	169
Figure B.14.1.1.1	PDAI Score and PRN Dose Level By Study Day – Panel Plots (mITT Population)	170
Figure B.14.3.2.1	Scatter Plots of Peak TBL vs Peak ALT for Identification of Drug Induced Liver Injury (DILI) (Safety Population).....	171

Table B.14.1.1.1 Patient Disposition – Completion Status (Screening Population)

	Number of patients (%)		
	Starting Dose 400 mg QD (N = n)	Starting Dose 400 mg BID (N = n)	Overall (N = n)
Screening population – Enrolled	n	n	n
ITT population – Had at least one dose of PRN1008 [1]	x (x.x)	x (x.x)	x (x.x)
Safety population – Had at least one dose of PRN1008 [1]	x (x.x)	x (x.x)	x (x.x)
mITT population – Treated up to Week 5 and had a Week 5 CDA assessment [1]	x (x.x)	x (x.x)	x (x.x)
Completer population – Treated up to Week 25 and had a Week 29 CDA assessment [1]	x (x.x)	x (x.x)	x (x.x)
PP population – Had no major protocol deviations, completed Week 13/Day 85 visit and had at least 80% study drug compliance [1]	x (x.x)	x (x.x)	x (x.x)
Completion status [2]			
Completed	x (x.x)	x (x.x)	x (x.x)
Early discontinuation	x (x.x)	x (x.x)	x (x.x)
Primary reason(s) for early discontinuation [3]			
Adverse Event	x (x.x)	x (x.x)	x (x.x)
Death	x (x.x)	x (x.x)	x (x.x)

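### Part B checks the Week 5 primary endpoint in Completer and per-protocol sets defined by events up to Week 29, and gives the per-protocol set two conflicting visit rules

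*SAP*

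**What the plan says.** **Endpoint.** Part B SAP 5.4.1 defines the primary efficacy endpoint as "The proportion of patients who are able to achieve CDA within 4 weeks (on or prior to Week 5 visit) of starting PRN1008 treatment" without prednis(ol)one above 0.5 mg/kg. The outcome is known at Week 5.

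**Sets used.** Part B SAP 5.4 makes mITT the set for all efficacy analyses, and 3.2.4 limits mITT to patients treated to Week 5 who have a Week 5 disease assessment. For the primary endpoint, 5.4.1 adds: "A sensitivity analysis using the Completer and PP population will be provided". Section 5.4.1.1 presents six subset analyses as an exploration of robustness and repeats both sets for each.

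**Membership.** Section 3.2.5 states: "Patients treated up to Week 25 and had a Week 29 disease assessment will be included in the Completer population". Section 3.2.6 requires, beside absence of major deviations and at least 80% compliance, "Completed Week 29 visit". The disposition text (5.1.1) and the footnote of Listing B.16.2.1.4 also say Week 29. The shell of Table B.14.1.1.1 and the footnote of Table B.14.1.1.4 instead say "completed Week 13/Day 85 visit and had at least 80% study drug compliance".

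**Part A.** The Part A SAP (4.3.5) requires "Completed Week 13/Day 85 visit" for PP. Its section 8 analyses ITT, mITT and PP side by side.

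**The concern.** A sensitivity analysis of a Week 5 proportion should vary an assumption about the Week 5 data. Here membership is decided by what happens afterwards, and the documents link later exit to response. Protocol 16.4 lets the investigator withdraw a patient for treatment failure. Part B SAP 5.1.1 codes lack of efficacy and progressive disease as reasons for discontinuation. Protocol Appendix 1B, criterion #2, stops PRN1008 when severe disease does not respond at the next review. If Week 5 non-responders leave more often than responders, the Completer and PP rates will exceed the rate in the patients who started treatment. Agreement between mITT, Completer and PP would then say little about robustness.

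The sets also move in one direction. Protocol 11.5.3 takes all dosed patients as the efficacy population. mITT is already narrower than that, and Completer and PP add later conditions. The Part B shells list the primary endpoint only for mITT, Completer and PP. The results are meant to inform the design of confirmatory trials, so the Week 5 rate will be used.

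The two PP rules are a separate defect: the tables that report the PP count use a different visit from the section that defines the set.

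**Working it through.** **1. The plan's own figure.** Part B SAP 2.3 says "If the clinical response rate is 50%, 25 subjects in each Part will result in an 80% CI of" ±13%. By the normal approximation, 1.2816 × √(0.5 × 0.5 / 25) = 0.128, or 12.8 points, so the figure reproduces. The SAP states no figure for the size of any analysis set.

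**2. Timing.**

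| Set | Condition | Weeks after Week 5 |
|---|---|---|
| Part A PP | Week 13 visit | 8 |
| Part B Completer | treated to Week 25, assessed at Week 29 | 20 and 24 |
| Part B PP, text and listing | Week 29 visit | 24 |
| Part B PP, two table shells | Week 13 visit | 8 |

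**3. Direction.** Let x of n patients respond at Week 5, let a be the share of responders who stay in the set, and b the share of non-responders who stay. The rate in the set is

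x·a / [x·a + (n − x)·b].

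This exceeds x/n only if a > b, and falls below it if a < b. The bias is therefore upward when non-responders leave more often. The documents make that plausible but give neither a nor b.

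**4. Size under assumed dropout.** Assume 12 responders among 25, the integer just below the planning rate of 50%, and 2 to 5 patients leaving after Week 5. Both are assumptions. Intervals are exact (Clopper-Pearson) 80% limits, the method named in Part B SAP 5.4: lower limit Beta(0.10; x, n − x + 1), upper limit Beta(0.90; x + 1, n − x).

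| Leavers | Rate in the set | 80% CI |
|---|---|---|
| none | 12/25 = 48.0% | 33.8% to 62.5% |
| 2, all non-responders | 12/23 = 52.2% | 37.0% to 67.0% |
| 3, all non-responders | 12/22 = 54.5% | 38.9% to 69.5% |
| 5, all non-responders | 12/20 = 60.0% | 43.3% to 75.1% |
| 5, of whom 2 responders | 10/20 = 50.0% | 33.8% to 66.2% |
| 2, both responders | 10/23 = 43.5% | 29.0% to 58.9% |

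The largest upward shift shown is 60.0 − 48.0 = 12.0 points, close to the planned half-width of 12.8. The last row moves down by 4.5 points.

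**5. The missing-data rule.** Part B SAP 5.4.1 counts unknown Week 5 status as non-response. Every patient in mITT must have a Week 5 assessment, so that rule has little or no effect there. It would act in an all-dosed analysis, which the shells do not list for this endpoint.

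**The case against.** Much can be said against a stronger version of this point, and most of it stands.

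- **Only upward?** A reader might infer that the sets drop failures and keep successes. A Week 5 responder remains one even if control is later lost (5.4.1), so a responder who relapses and leaves is removed as a success. The discontinuation reasons also include adverse event, subject withdrawal, non-compliance and recovery, any of which can remove responders.
- **Are Week 5 failures taken off drug by rule?** Protocol Appendix 1A says "If not responding, commence conventional immunosuppressive therapy and discontinue PRN1008", including under criterion #3 for patients without CDA by 4 weeks. That appendix governs Part A, and the step follows a later review. In Part B, criterion #3 of Appendix 1B contains no stopping step. The same instruction appears there under criterion #2, for severe disease.
- **PP asks for a visit, not continued treatment.** A patient off drug who attends Week 29 can still qualify if compliance suffices, and Protocol 16.4 asks that follow-up be completed where possible. Completer is the stricter filter.
- **Part A.** It does not call PP a sensitivity analysis, and its ITT result counts unknown Week 5 status as non-response.
- **Is the PP result irreproducible?** Three places agree on Week 29, and Part B SAP section 6 allows the shells to be adjusted. The Week 13 wording matches the Part A definition and may be carried over from it. The intended rule is identifiable, though the text still needs correcting.

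One may add that this is an open-label pilot with no hypothesis testing in Part B. That lowers the stakes, but does not make selection after the endpoint a test of robustness.

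**Conclusion.** The point holds for Part B in two respects. First, the Week 5 endpoint and its six subset analyses are checked in sets whose membership depends on events up to 24 weeks after the outcome. This may bias the rate, probably but not certainly upward. Under the assumed dropout the rate moves from 48.0% to anywhere between 43.5% and 60.0%, and the actual size cannot be computed because the documents give no dropout rate. Larger shifts can be produced by letting many non-responders and no responders leave, but nothing in the documents supports that pattern as the expected one. Second, the PP set has two visit rules in current text of the same SAP, so the PP count reported can differ from the set analysed.

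Part A PP shares the first feature at Week 13 but sits beside an ITT analysis, so less depends on it. The more important gap in Part B is that no listed table gives the primary endpoint in all dosed patients. The plan should be changed, though the main mITT result does not depend on the Completer or PP sets.

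**What to change.** 1. For the Week 5 endpoint and its subsets, define PP by major deviations and at least 80% compliance from Day 1 to the Week 5 visit. Drug reconciliation is already scheduled at Day 15 and Day 29.
2. Keep the Completer set for the 24-week endpoints, or label its Week 5 result supplementary rather than a sensitivity analysis.
3. Add a Part B table of the primary endpoint in the ITT (all-dosed) population, counting unknown Week 5 status as non-response as 5.4.1 already provides.
4. State one PP visit condition in 3.2.6, 5.1.1, Table B.14.1.1.1, the footnote of Table B.14.1.1.4 and the footnote of Listing B.16.2.1.4. If a later-visit PP set is kept for the 24-week endpoints, give it its own name and flag.

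The cost is SAP wording, re-derived population flags and a few tables. No new data are needed.

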3.2.7 Pharmacokinetic Analysis Population

The Pharmacokinetic Analysis Population will be described in the PK SAP, a separate document.

3.4 Analysis Timepoints and Definitions

The study visits in Part B are:

- SCREENED
- WEEK 1 DAY 1
- WEEK 1 DAY 2
- WEEK 3 DAY 15
- WEEK 5 DAY 29

- WEEK 9 DAY 57
- WEEK 13 DAY 85
- WEEK 17 DAY 113
- WEEK 21 DAY 141
- WEEK 25 DAY 141
- WEEK 25 DAY 169
- UNSCHEDULED

All scheduled visits will be summarized. 'Last Visit' will be summarized for selected parameters and is defined as the last non-missing post-baseline visit, including unscheduled visits.

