16.10 ECG Procedures

Single 12-lead ECG assessments will be obtained as specified in the Schedule of Assessments ([Appendix 4](#)) to confirm eligibility and to ensure real time safety evaluation of the participants in the study, as specified in the Schedule of Assessments. Unscheduled ECGs may be performed as clinically indicated and recorded in the eCRF.

Participants should be in a resting position for at least 10 minutes prior to any measurement. Body position should also be consistently maintained for each ECG evaluation. In particular, changes in heart rate should be avoided. There should be no environmental distractions (TV, radio, conversation) during the pre-ECG rest and the ECG recording time.

Heart rate (HR), QRS duration and respiratory rate (RR), and QT intervals will be recorded. Changes of the T-wave and U-wave morphology and overall ECG interpretation will be documented.

All ECG recordings must be performed using a standard high-quality, high-fidelity digital electrocardiograph machine equipped with computer-based interval measurements.

For safety monitoring purposes, the Investigator must review, sign and date all ECG tracings. Paper copies will be kept at the study center with the participant's clinical file as part of the permanent record. The ECG intervals and interpretation will be recorded on the CRF.

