5.5.3 Vital Signs and Body Weight

Vital signs include blood pressures (BP), pulse, temperature and respiratory rate and body weight are measured at visits specified in the Schedule of assessments (Table 1).

The actual values and change from baseline values will be summarized by dose level and overall for each visit. A separate table will be generated to include only the baseline, Day 85, Day 169 and Day 197 visits.

The following ranges will be used to classified the BP and pulse measurements as Low/Normal/High:

- Systolic blood pressure (SBP): 90 to 140 mmHg, inclusive
- Diastolic blood pressure (DBP): 60 to 80 mmHg, inclusive
- Pulse: 40 to 100 bpm, inclusive

Shift from baseline tables will be produced by using the above criteria.

Patient data listings will be provided for the vital sign parameters and body weight. Separate listings will be provided for patients with out of range SBP, DBP or pulse results at any visits.

5.5.4 12-Lead ECG

ECG assessment is performed at the screening visit and unscheduled visit, if clinically indicated.

The ECG parameters include: normal sinus rhythm? (yes or no), ventricular rate, P-R interval, QRS interval, QT duration, QTcF, QTcB interval and overall ECG interpretation (normal, abnormal – not clinically significant (NCS) or abnormal – clinically significant (CS)).

For the numerical values, actual values will be summarized by descriptive statistics for each dose level and overall. For normal sinus rhythm and ECG interpretation, the results will be tabulated by each dose level and overall in a shift from baseline table.

A patient data listing will be provided for the ECG results.

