Median	x.xx	x.xx	x.xx	x.xx
Min, Max	x.x, x.x	x.x, x.x	x.x, x.x	x.x, x.x
LAST VISIT*				
n	x	x	x	x
Mean (SD)	x.xx (x.xxx)	x.xx (x.xxx)	x.xx (x.xxx)	x.xx (x.xxx)
Median	x.xx	x.xx	x.xx	x.xx
Min, Max	x.x, x.x	x.x, x.x	x.x, x.x	x.x, x.x
LAST VISIT* – CHANGE FROM BASELINE				
n	x	x	x	x
Mean (SD)	x.xx (x.xxx)	x.xx (x.xxx)	x.xx (x.xxx)	x.xx (x.xxx)
Median	x.xx	x.xx	x.xx	x.xx
Min, Max	x.x, x.x	x.x, x.x	x.x, x.x	x.x, x.x

Patients are classified into different dose levels according to the dose they received at a given visit.

*LAST VISIT is the last post-baseline visit.

Program: <program name (date, time)>, Path: <path>

Table B.14.3.8.3 12-Lead ECG – Overall Assessment – Shift from Baseline to Last Post-Baseline Visit (Safety Population)

Parameter = Parameter x [unit]

Post-baseline	Overall (N = n)			
	N assessed	Low	Normal	High
LAST VISIT	n	x (x.x)	x (x.x)	x (x.x)
Low	x (x.x)	x (x.x)	x (x.x)	x (x.x)
Normal	x (x.x)	x (x.x)	x (x.x)	x (x.x)
High	x (x.x)	x (x.x)	x (x.x)	x (x.x)

Patients are classified into different dose levels according to the dose they received at a given visit.

Program: <program name (date, time)>, Path: <path>

Programming notes:

- Repeat table for the 400 mg QD, 400 mg BID and 600 mg BID.
- Highlight Normal to Low/High shifts in yellow. Do not display 0 (0.0)% for zero count for shifts.

Table B.14.3.9.1 Abbreviated Physical Examination by Study Visit (Safety Population)

Body System	Study Visit	N attended visit/ Result	400 mg QD (N = n)	400 mg BID (N = n)	600 mg BID (N = n)	Overall (N = n)
General Appearance	SCREENED	N attended visit	x	x	x	x
		Normal	x (x.x)	x (x.x)	x (x.x)	x (x.x)
		Abnormal NCS	x (x.x)	x (x.x)	x (x.x)	x (x.x)
		Abnormal CS	x (x.x)	x (x.x)	x (x.x)	x (x.x)
		Not None	x (x.x)	x (x.x)	x (x.x)	x (x.x)
	WEEK 1 DAY 1	N attended visit	x	x	x	x
		Normal	x (x.x)	x (x.x)	x (x.x)	x (x.x)
		Abnormal NCS	x (x.x)	x (x.x)	x (x.x)	x (x.x)
		Abnormal CS	x (x.x)	x (x.x)	x (x.x)	x (x.x)
		Not None	x (x.x)	x (x.x)	x (x.x)	x (x.x)
	WEEK 3 DAY 15	N attended visit	x	x	x	x
		Normal	x (x.x)	x (x.x)	x (x.x)	x (x.x)
		Abnormal NCS	x (x.x)	x (x.x)	x (x.x)	x (x.x)
		Abnormal CS	x (x.x)	x (x.x)	x (x.x)	x (x.x)
		Not None	x (x.x)	x (x.x)	x (x.x)	x (x.x)
...etc...						

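### Part B summarises ECGs at the last post-baseline recording only, so a clinically significant ECG followed by a better repeat drops out of both ECG summary tables; separately, the shift table has no cell for an abnormal interpretation

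*SAP*

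**What the plan says.** **When ECGs are taken.** Section 5.5.4 of the Part B SAP states: "ECG assessment is performed at the screening visit and unscheduled visit, if clinically indicated". Its Schedule of Assessments (Table 1) agrees: apart from screening, the ECG row is marked only in the unscheduled column, with a footnote limiting it to clinical indication. Protocol Section 16.10 says the same: "Unscheduled ECGs may be performed as clinically indicated and recorded in the eCRF".

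**How they are to be summarised.** For the categorical results, Section 5.5.4 says: "For normal sinus rhythm and ECG interpretation, the results will be tabulated by each dose level and overall in a shift from baseline table". It names no post-baseline time point. The time point comes from the shells. Table B.14.3.7.1 (numeric values) has a screening block and a last-visit block, with the footnote "LAST VISIT is the last post-baseline visit". The title of Table B.14.3.8.3 (overall assessment) limits it to the shift from baseline to the last post-baseline visit. Section 3.4 defines the term for selected parameters: Last Visit "is defined as the last non-missing post-baseline visit, including unscheduled visits".

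**Categories.** Section 5.5.4 lists three grades of overall interpretation: normal, abnormal NCS and abnormal CS. The rows and columns of Table B.14.3.8.3 are Low, Normal and High, and its programming note repeats this: "Highlight Normal to Low/High shifts in yellow".

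**The concern.** The last value is a reasonable summary when everyone is measured on a common schedule. Here nobody is. A post-baseline ECG exists only because something prompted it, and a natural reason for a further one is to recheck an abnormal tracing. In that sequence the last-visit rule keeps the recheck and discards the tracing of interest, together with its QTcF.

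The dose column can also mislead. Both shells classify patients by the dose received at the given visit, and the Last Visit definition is not restricted to time on treatment. In a design with dose escalation from the Week 3 visit, the last ECG can fall under a different dose from the event.

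Safety is a primary objective, and QTc prolongation, poorly controlled atrial fibrillation and other clinically significant ECG abnormalities are grounds for exclusion (protocol Section 6.2, criterion 3). Tables B.14.3.7.1 and B.14.3.8.3 are the only planned ECG summaries after screening, so a reader of the tables alone could see no shift where a clinically significant one had occurred.

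**Working it through.** The plan states no sample size, rate or threshold on this point, so there is no figure to reproduce. The check is to apply the rules to possible ECG sequences.

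**Inputs**
- Baseline: the screening ECG (Table B.14.3.7.1).
- Post-baseline ECGs: unscheduled only (Section 5.5.4 and Table 1).
- Planned rule: keep the last non-missing post-baseline ECG (Section 3.4 and both shells).
- Comparison rule: keep the worst post-baseline ECG, ranked CS over NCS over normal (the grades of Section 5.5.4).

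**Applied to illustrative sequences** (assumed for the check, not trial data; screening first)

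| Sequence | Last-visit rule | Worst-post-baseline rule |
|---|---|---|
| Normal, CS, Normal | Normal to Normal | Normal to CS |
| Normal, CS, NCS | Normal to NCS | Normal to CS |
| Normal, CS (no repeat) | Normal to CS | Normal to CS |
| Normal (no later ECG) | not assessed | not assessed |

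The two rules differ only in the first two rows, where a later ECG is read as normal or less severe. In each of those rows the count of shifts to CS is 0 under the plan and 1 under the comparison rule. The numeric table behaves in the same way: only the intervals of the final ECG enter it.

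**The category mismatch is independent of this.** In the third row both rules give CS, yet a grid of Low, Normal and High has nowhere to put it. The NCS result in the second row has no cell either. Of the three grades in Section 5.5.4, only normal fits the printed table.

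**Comparison with the rest of the Part B safety plan**
- Liver tests: Table B.14.3.4.3 counts a patient who meets a criterion during the treatment period, under the dose at that time.
- Liver scatter plot: Figure B.14.3.2.1 uses the peak value on a given dose.
- Adverse events: Section 5.5.1 counts each patient at maximum grade.

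A worst-value rule for ECG would follow the practice the SAP already uses for these data.

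**The case against.** The strongest reply is that nothing is lost. Listing B.16.2.8.15 shows each ECG. Listing B.16.2.8.16 isolates patients with any abnormal ECG and highlights CS readings. With about 25 patients planned in Part B and ECGs taken only on indication, those listings may be short. Protocol Section 12.7 also asks for a clinically significant ECG to be recorded as an adverse event if it comes with symptoms or leads to a change in study drug or concomitant therapy. Both listings carry a column linking a CS reading to an adverse event number, and such an event would be counted in the treatment-emergent adverse event tables under the dose at onset. This stands, and it limits the point: a reader might infer that the event disappears from the report, and the documents do not support that. What the tables still omit is the interval values of the triggering ECG and any CS reading that does not meet the Section 12.7 conditions.

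Second, a reader might infer that the last ECG is always the recovery tracing, or that the Low/Normal/High labels cause the masking. Neither follows. Without a repeat, the abnormal ECG is itself the last one, and the labels are a separate defect.

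Third, the last-visit restriction for ECG sits in the shells, and Section 6 lets their layout be adjusted to the data collected. That makes correction easy. It does not replace a stated last-visit rule with a different one, and in an open-label study the choice between last and worst is better made before the data are seen.

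Fourth, maximum QTcF tends to rise with the number of ECGs taken, so it is also a selected summary. That is correct and should be stated with the table. Finally, Section 4.1 does not name ECG among the components of the safety endpoint, which lowers the weight of the point.

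**Conclusion.** The point holds for the two ECG summary tables and not for the report as a whole. Followed as written, the plan tabulates a clinically significant ECG with a normal repeat as Normal to Normal, and one with a less severe repeat as the lesser grade. Each such patient lowers the CS shift count by one. This rests on one assumption: that a later and less severe ECG was recorded. The documents give no frequency for repeat ECGs, so no percentage should be attached. Dividing one hypothetical case by the planned 25 would give an apparent rate that the documents do not support.

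The category mismatch needs no assumption. It is a direct contradiction between Section 5.5.4 and Table B.14.3.8.3, and it affects every abnormal interpretation, resolved or not.

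It is also tempting to read the Average/Worst finding row in Listing B.16.2.8.15 as already supplying the worst ECG. It does not: the row summarises tracings within one visit. Overall this is an inexpensive improvement worth making, partly mitigated by the listings and adverse event recording.

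**What to change.** - **Table B.14.3.8.3:** tabulate the worst post-baseline interpretation (CS over NCS over normal) in the categories Normal, Abnormal NCS and Abnormal CS. Attribute it to the dose being taken when that ECG was recorded. Use the number of patients with any post-baseline ECG as the denominator, and report that number.
- **Table B.14.3.7.1:** add maximum post-baseline QTcF and maximum increase from screening. Note that these come from a subset selected by clinical indication, with unequal numbers of ECGs per patient.
- **Derivation:** take the worst value across all recorded ECGs for the patient, not from the within-visit listing row.
- **Text:** state the rule in Section 5.5.4, so that it does not depend on the shells.

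The cost is a small amount of reprogramming and some shell and footnote wording. No extra ECGs or data collection are needed. The tables may look slightly less favourable.
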